Sample Size Calculation (This has NOT changed from original IRB): The sample sizes are calculated separately for the two risk groups (650 in surveillance group and 650 in screening group). Among the surveillance group, we want to test non-inferiority in sensitivity and superiority in specificity of LCE+HRME vs. LCE alone. The standard endoscopic evaluation using LCE has high sensitivity of about 95% but with low specificity at about 65%. Based on the preliminary data, we hypothesize that LCE+HRME has the sensitivity of at least 90% level, which is similar to that of LCE, but LCE+HRME would improve the specificity to 85%. With significance level of 0.05 and 80% power, we need 223 neoplastic patients and 65 benign patients in each arm (LCE and LCE+HRME) to conclude that LCE+HRME has similar sensitivity as LCE alone and had higher specificity than LCE alone. Hence, we need 446 neoplastic patients and 130 benign patients. The sample size calculation is based on the formula in Pepe (Chapter 8, The statistical Evaluation of Medical Tests for Classification and Prediction, 2003).

According to the preliminary results, greater than 80% patients in the surveillance group would have neoplasia. We anticipate the enrollment of total 650 patients in the surveillance group to ensure the accrual of 446 neoplastic patients and 130 benign patients.

In screening group, we will study the accuracy of LCE+HRME for the diagnosis of neoplasia, and test whether the negative predictive value (NPV) of LCE+HRME is higher than LCE alone. The NPV for using LCE alone is about 95%. We hypothesize that the NPV for LCE+HRME should be at least 99% to be useful. A sample of 300 per arm would provide 82.1% power for this hypothesis with a 5% type-I error. Assuming an 8% loss to follow-up or incomplete data, we need to recruit 325 subjects per arm in the screening population.

Power Calculation (Augmented Reality HRME Revision): We anticipate having at least 400-500 subjects remaining by the time the Augmented Reality HRME revision IRB is approved and funding from the NCI obtained. With 400 patient Augmented Reality HRME data, assuming an accuracy of 83% AND 650 LC patient, assuming an accuracy of 57%, the study should have >93% power to detect a statistically significant difference with an alpha error rate of 0.05.

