For the HRME image interpretation study, the sample size of 10 endoscopists was selected based on a prior power analysis based on non-inferiority. The 10 endoscopists will review about 140 HRME images. It is hypothesized that software interpretation of the HRME images will be non-inferior to the endoscopist interpretation. Non-inferiority is defined as a 10% difference in specificity between the two groups with 90% power and alpha of 0.05.

G2. Data Analysis

Provide a description of your plan for data analysis. State the types of comparisons you plan (e.g. comparison of means, comparison of proportions, regressions, analysis of variance). Which is the PRIMARY comparison/analysis? How will the analyses proposed relate to the primary purposes of your study?

Among the surveillance group, three analyses in testing the null hypotheses will be performed, including two interim analyses and one final analysis. The analysis will be performed when 220, 440 and 650 study subjects have been accrued, respectively.

The interim analysis will use a symmetric two sided group sequential design using a Hwang-Shih-DeCani spending function with beta spending of .4, which provides an O'Brien-Fleming-like conservative upper bound. This approach requires a two sided significance level of 0.0026 and 0.0114 for the interim analysis and 0.0464 for the final analysis of overall survival.

There will be no interim analysis for the screening population.

The primary analysis for the surveillance group is to test non-inferiority in sensitivity and superiority in specificity of LCE+HRME vs. LCE alone. The test statistic is based on the formula in Pepe (Chapter 8, The statistical Evaluation of Medical Tests for Classification and Prediction, 2003). Additionally, sensitivity and specificity of LCE+HRME vs. LCE alone will be estimated on a per patient basis with 95% confidence intervals. The primary goal for the screening group is to test whether the negative predictive value (NPV) of LCE+HRME is higher than LCE alone. This is done using Fisher's exact test. Additionally, the negative predictive value will be summarized with 95% confidence intervals.

The secondary analysis includes diagnostic yield, clinical efficiency, clinical impact, progression rate, and the rate of adverse events.

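### The 82.1% power for the screening NPV comparison comes from an uncorrected z-test approximation; the planned Fisher's exact test, if two-sided, has 79.8% on the same inputs, a small misstatement to correct.

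*Combined protocol and SAP*

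**What the plan says.** Section G1 (Sample Size) sizes the screening group separately from the surveillance group. For the control arm: "The NPV for using LCE alone is about 95" per cent. For the experimental arm: "We hypothesize that the NPV for LCE+HRME should be at least 99% to be useful". The power claim is: "A sample of 300 per arm would provide 82.1% power for this hypothesis with a 5% type-I error". Recruitment is then inflated: "Assuming an 8% loss to follow-up or incomplete data, we need to recruit 325 subjects per arm in the screening population". G1 does not say which test produced the power figure, or whether it is one- or two-sided.

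Section G2 (Data Analysis) gives the primary screening goal as to "test whether the negative predictive value (NPV) of LCE+HRME is higher than LCE alone" and then says: "This is done using Fisher's exact test". No sidedness or one-sided alpha is given there either. G2 also says: "There will be no interim analysis for the screening population". The whole 5% is therefore available at the single final analysis.

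**The concern.** A power statement should describe the test that will be run. Fisher's exact test is conservative when events are few, and they are few here: at 300 per arm the assumed NPVs imply about 15 false negatives with Lugol's alone (300 × 0.05) and about 3 with HRME added (300 × 0.01). Power from an uncorrected normal approximation can therefore overstate what Fisher's test delivers. At stake is whether the one power figure for the screening group's primary comparison belongs to its planned analysis, and how large the difference is.

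**Working it through.** **Inputs, all from G1 and G2.** NPV 0.95 (Lugol's alone) and 0.99 (Lugol's plus HRME); 300 per arm, equal allocation; alpha 0.05; no interim look. Sidedness is not stated.

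**Step 1: reproduce 82.1%.** For the pooled z-test without continuity correction, two-sided:

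- Mean proportion: (0.95 + 0.99)/2 = 0.97.
- Null standard error: √(2 × 0.97 × 0.03/300) = 0.01393.
- Alternative standard error: √((0.95 × 0.05 + 0.99 × 0.01)/300) = √(0.0574/300) = 0.01383.
- Power = Φ[(0.04 − 1.960 × 0.01393)/0.01383] = Φ(0.918) = 0.8207.

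This is the stated 82.1%. Other approximations do not give it:

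| Approximation | Power |
|---|---|
| Unpooled z, two-sided | 82.4% |
| Pooled z, one-sided | 89.2% |
| Arcsine, two-sided | 86.7% |
| Continuity-corrected pooled z, two-sided | 75.1% |
| Continuity-corrected pooled z, one-sided | 84.0% |

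**Step 2: exact power of the planned test.** Let X ~ Bin(300, 0.05) and Y ~ Bin(300, 0.01) be the false-negative counts. Power is the sum of P(X = x)P(Y = y) over all pairs (x, y) for which the test gives p ≤ 0.05. Size is the same sum with a common false-negative rate in both arms.

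| Test, 300 per arm | Exact power | Exact size, NPV 99% to 95% |
|---|---|---|
| Fisher, two-sided 0.05 | 79.8% | 1.2% to 3.2% |
| Fisher, one-sided 0.05 | 87.6% | 1.5% to 3.2% |
| Fisher mid-p, two-sided | 85.3% | at most 4.9% |
| Pooled chi-square, two-sided | 86.4% | up to 5.1% |

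The two-sided gap is 82.1 − 79.8 = 2.3 percentage points.

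**Step 3: numbers per arm for two-sided Fisher.**

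| Evaluable per arm | Power |
|---|---|
| 299 (325 × 0.92) | 79.6% |
| 300 | 79.8% |
| 302 | 80.1% |
| 314 | 82.0% |
| 315 | 82.2% |
| 325 (no loss) | 83.7% |

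**Step 4: the denominator.** Steps 1 to 3 take every evaluable patient as test-negative. NPV is computed only among test-negatives, and the documents give no test-negative rate. As an assumed range, two-sided Fisher and mid-p powers are:

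| Test-negatives per arm (assumed) | Fisher | Mid-p |
|---|---|---|
| 270 | 74.1% | 80.8% |
| 200 | 56.3% | 65.9% |
| 150 | 39.6% | 50.9% |

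**The case against.** The strongest reply is that this is immaterial. The gap is 2.3 points. G1 sets no power target for screening, since its 80% belongs to the surveillance calculation. Two more evaluable patients per arm bring Fisher past 80%, and if all 325 recruited per arm were evaluable it would have 83.7%, above the stated figure. This stands as a limit on the weight of the point. It does not make 82.1% the power of Fisher's test.

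Second, sidedness is not stated and the G2 hypothesis is worded directionally. That also stands: 79.8% depends on a two-sided test, inferred from the match in step 1. A one-sided reading gives 87.6%, which is not 82.1% either, so the mismatch does not depend on the inference. Its direction and size do.

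Third, a reader might infer from the 1.2% to 3.2% size that the plan fails to deliver its 5% type I error, or that Fisher's test throws power away for no gain. The documents do not support either reading. The 5% is a nominal ceiling and Fisher's test keeps below it. What it buys is guaranteed control, a recognised choice for a primary comparison with few events. Nor is a replacement free. Pooled chi-square slightly exceeds 5% within the planned NPV range. Mid-p stays below 5% there with 300 in each arm but has no general guarantee: its maximum over all null rates is 5.2%. With unequal test-negative counts, say 120 and 270 (assumed for illustration), it reaches 5.5% over NPV 95% to 99%, where Fisher stays at 3.9%.

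Finally, the denominator matters far more than the choice of test. That is true, but it is a separate issue, and resolving it would leave this mismatch in place.

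**Conclusion.** The point holds as a small misstatement of power. The 82.1% in G1 is a two-sided uncorrected pooled z-test approximation, while the test named in G2 has 79.8% power on the same inputs if two-sided, and 87.6% if one-sided at 0.05. The planned analysis is valid, and the 2.3-point gap does not by itself call for more patients. These figures rest on NPVs of 95% and 99%, independent arms, two-sided testing for the 79.8%, and all 300 per arm counting in the NPV denominator. The last assumption is the weakest, and any restated figure should carry it openly.

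**What to change.** In G1, name the test and sidedness behind the screening power figure, and restate it as 79.8% for a two-sided Fisher's exact test at 0.05 with 300 per arm and NPVs of 95% and 99%. Add that the figure assumes all 300 per arm are test-negative and so enter the NPV denominator. State the same sidedness in G2. If a one-sided 0.05 test is intended, say so in both places and give 87.6%.

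As an option, prespecify the mid-p version of Fisher's test in G2. With 300 per arm this gives 85.3% power and size of at most 4.9% over NPV 95% to 99%. The price is the loss of guaranteed type I error control, particularly if test-negative counts differ between arms. Keeping Fisher's test is equally defensible.

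The cost is a clause in G1 and a line in G2, with no extra patients, procedures or data. No stopping boundary is affected, because the screening group has no interim analysis.

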The overall objective of this multicenter trial is to determine whether use of a low-cost, high-resolution microendoscope during diagnostic upper endoscopy can improve the efficiency and accuracy of endoscopic screening for esophageal squamous cell neoplasia (ESCN). This is a trial of a novel technology, a miniaturized, low cost (<\$3,500) microscope device which can be used during upper endoscopy to image the gastrointestinal epithelium. This portable, battery-operated high-resolution microendoscope (HRME) was developed by our collaborators at Rice University and provides greater than 1000X magnified images of the esophageal mucosa. In a single-arm, pilot study of the device in an enriched population of 60 high-risk subjects in China and the US, we used the microendoscope during routine Lugol's chromoendoscopic screening to categorize areas of abnormality (unstained areas). The sensitivity /specificity for the device seen in this study were 100% and 79%-a significant improvement over the sensitivity/specificity of Lugol's chromoendoscopy which were 97% and 52%. Thus, our presumption is that HRME can enhance the specificity (and lower the false positive rate) of Lugol's. As part of a National Cancer Institute R01 supplement (Figure 1), we have enhanced the current HRME technology by introducing an automated, ergonomic, augmented reality platform. The augmented reality platform displays, in real-time, the microscopic image colocalized with the endoscopic image, potentially allowing more targeted biopsies/treatment and increased accuracy. Our central hypothesis is that our approach can improve the efficiency and clinical impact of endoscopic screening and surveillance of ESCN by providing *in-vivo* optical biopsies comparable to standard histology. Specifically, HRME will facilitate accurate, rapid real-time endoscopic screening by non-expert clinicians. We also hypothesize the HRME will provide additional, more accurate information regarding the presence of neoplasia that will impact upon the physician's decision to obtain a mucosal biopsy or perform endoscopic therapy (endoscopic mucosal resection or ablation). This could potentially minimize the number of unnecessary biopsies and enable the physician to perform endoscopic therapy at the time of the initial examination, rather than delaying endoscopic treatment to another procedure following pathologic confirmation of the initial biopsies. We will compare (1) the current endoscopic "standard of care" (white light endoscopy with Lugol's iodine), (2) HRME with subjective, human interpretation, and (3) augmented reality HRME (software, 'machine' interpretation). The addition of (3) is the basis for our revision R01 and this amended IRB. The accuracy, efficiency, clinical impact and cost-effectiveness of each approach in the diagnosis and management of ESCN will be determined in both the Chinese and US healthcare systems. Specific endpoints: 1. Efficiency: (a) Diagnostic Yield: The number of neoplastic biopsies/total number of biopsies obtained in patients who receive biopsies. (b) 'Patients saved': Number of patients who receive no biopsies (c) Procedure time: Total procedure time in each group 2. Clinical impact: Determine potential clinical impact of HRME by determining if use of the device (with both subjective and automated read) changes the decision to perform endoscopic therapy and perform, or not perform, a mucosal biopsy when compared to LC alone. 3. Prospectively compare the performance characteristics of HRME-LC to LC for the prediction of squamous esophageal neoplasia in flat mucosa and mucosal lesions using histopathology as the gold standard. (a) Determine the sensitivity, specificity, positive and negative predictive value for the identification of neoplasia on a per biopsy and per patient analysis. 4. Determine the cost-effectiveness of HRME-LC to LC alone for the endoscopic screening and surveillance of ESCN in the US and China.

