In both groups, per standard of care, endoscopic examination will be performed using white-light endoscopy with Lugol's dye-spray. In each subject, the location of each unstained area (level, quadrant) will be recorded and digital images obtained. The endoscopist's clinical impression will be recorded for each Lugol's abnormal area and visible lesion ('nonneoplastic' vs. 'neoplastic') as well as his/her proposed plan: a. no biopsy, b. biopsy, c. endoscopic treatment/removal. In the standard-of-care arm (Group B), biopsies will be obtained of all Lugol's abnormal areas. Likewise, Group A will receive the clinician subjective HRME read + augmented reality software HRME read, sequentially, of all Lugol's unstained (abnormal) areas prior to tissue biopsy. For imaging, 1-10 ml proflavine hemisulfate (0.01%) will be sprayed on the esophageal mucosa. The HRME probe placed gently on the mucosa and the augmented reality microscopic (HRME) image displayed on the glasses, with the endoscopic image (monitor) behind it. The endoscopist will first make a subjective interpretation (neoplasia vs. no neoplasia) and plan of action (biopsy, no biopsy, treat) WITHOUT the image-analysis software. Once this qualitative ("Human") read is recorded, the image analysis software will be turned on and the software diagnosis provided in real-time. This quantitative ("Machine") read and the revised plan of action will be recorded. The HRME procedure (including Human and Machine reads) as well as standard endoscopy and biopsy time will be recorded. The research coordinators will indicate the biopsy number/location on an esophageal map diagram. The biopsies from each site will be placed in formalin per standard of care and labeled according to biopsy location (quadrant: 12, 3, 6, 9 o'clock). In all subjects, all Lugol's abnormal areas will be biopsied (to uphold the standard of care, per IRB); however, HRME "non-neoplastic" sites will be considered not tissue-biopsied for purpose of the analysis. All biopsies will be submitted for consensus diagnosis by 2 expert GI pathologists.

A schematic of the existing trial with the proposed revision is shown in Figure 2. The IRB revision is shown in RED. We anticipate that this revision will add an additional 30-60 seconds per procedure but will otherwise not change patient care.

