Diagnostic yield: This is defined as the proportion of all biopsies that are truly neoplastic over the total number of biopsies obtained in patients who receive biopsies. A generalized linear model for logistic regression with multiple correlated binary outcomes within each patient will be used for data analysis. In this model the binary outcome for each biopsy specimen is whether the specimen is neoplastic or non-neoplastic, and the explanatory variable is the arm (LCE+HRME vs. LCE alone) stratified by group (screening and surveillance). PROC GLIMMIX in SAS will be used because of the correlations among samples from the same patient. The model will allow for testing whether the proportion of samples classified as neoplasia differs between the 2 arms.

'Clinical efficiency': For patients that have benign disease confirmed by histology, the true proportion of patients potentially saved any biopsy using HRME (Lugol's + and HRME -) will be estimated by 95% confidence intervals (stratified by group). Proportions will be compared between groups by the chi-square test or Fisher's exact test. Procedure time in the HRME+LC arm will be compared to the LC arm by analysis of variance, stratified by group (screening and surveillance). An interaction term will also be included to determine to what extent the difference in procedure time between the 2 arms varies between the 2 risk groups.

Clinical impact: For this, the proportion of patients who had a change in the decision to perform endoscopic therapy or mucosal biopsies as a result of LCE+HRME or LCE alone, will be estimated by a 95% confidence interval. This proportion will be compared between LCE+HRME and LCE alone by the chi-square test or Fisher's exact test.

Progression rates: Five year follow-up of progression rates to more advanced pathology or esophageal cancer (EC) in the 2 arms will be conducted. Progression rates and their 95% confidence interval will be summarized and compared between LCE+HRME and LCE alone by the chi-square test or Fisher's exact test.

Safety/Adverse Events: Immediate and 48 hour adverse event (AE) rates will be compared between the LCE+HRME arm and LCE alone arm by the chi-square test or Fisher's exact test. The AE rates and their 95% confidence intervals will be summarized.

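### Clinical impact counts any changed decision, whatever its direction or histology, so it cannot show better decisions and rises as HRME sensitivity falls

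*Combined protocol and SAP*

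**What the plan says.** Section D lists clinical impact as the second of four endpoints. It asks whether use of the device, with both the subjective and the automated read, "changes the decision to perform endoscopic therapy and perform, or not perform, a mucosal biopsy when compared to LC alone". The same section gives the rationale: "HRME will provide additional, more accurate information regarding the presence of neoplasia that will impact upon the physician's decision", and "This could potentially minimize the number of unnecessary biopsies".

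Section G2 turns this into an analysis of "the proportion of patients who had a change in the decision to perform endoscopic therapy or mucosal biopsies", estimated with a 95% confidence interval. It adds: "This proportion will be compared between LCE+HRME and LCE alone by the chi-square test or Fisher's exact test". Nothing there separates one direction of change from another or refers to the pathology result. G2 says that diagnostic yield and clinical efficiency are stratified by risk group, but does not say so for clinical impact.

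The neighbouring clinical-efficiency analysis does use pathology: "For patients that have benign disease confirmed by histology, the true proportion of patients potentially saved any biopsy using HRME".

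Section F2 records a plan (no biopsy, biopsy, or treatment) after Lugol's staining in both groups. In the HRME group it records a further plan after the human read and a revised one after the software read. HRME is applied only to areas left unstained by Lugol's. All such areas are biopsied in every subject whatever the HRME read, and two pathologists give a consensus diagnosis.

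**The concern.** The rationale is that decisions change because the information is better. A raw change rate cannot test that, because a correct omission of biopsy and an omission in a patient with neoplasia each add one to the numerator.

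The effect should be largest in the surveillance group, where G1 expects that "greater than 80% patients in the surveillance group would have neoplasia". HRME is read only on Lugol's-abnormal areas, so with regard to biopsy it acts mainly to remove sites. A less sensitive read removes more of them, and the endpoint goes up. A larger clinical impact could then be read as support for HRME-guided decisions when part of the increase reflects lost sensitivity.

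**Working it through.** **Inputs.** From G1: 650 surveillance patients; neoplasia above 80%, taken first as 80%; LCE sensitivity 95% and specificity 65%; LCE+HRME sensitivity at least 90% and specificity 85%. Assumptions: 1:1 allocation, so 325 per arm; Lugol's-positive means a plan to biopsy; HRME-negative means a plan of no biopsy; counting is per patient. G1 gives no figure for clinical impact.

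**Reproducing the G1 sample size.** This shows what role the 90% plays. For two independent arms on the log-ratio scale, n = (z_alpha + z_power)² × [(1−pA)/pA + (1−pB)/pB] / [ln(r1/r0)]². With one-sided alpha 0.05 and 80% power, (1.645 + 0.842)² = 6.18.

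- Sensitivity, both arms at 0.95, limit r0 = 0.90/0.95: 6.18 × 0.1053 / 0.002923 = 222.6, so 223.
- False-positive fraction, 0.35 to 0.15, r0 = 1: 6.18 × 7.524 / 0.7179 = 64.8, so 65.

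Both match the 223 and 65 per arm in G1. Of the variants tried, only this one gives both. The two-sided version gives 283 and 83, and non-inferiority on the absolute scale gives 235 (one-sided). So 90% works as the non-inferiority limit, with 95% as the planning value for both arms.

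**Expected net switches from biopsy to no biopsy, surveillance HRME arm.** With neoplasia prevalence π and LCE+HRME sensitivity Se:

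- neoplastic patients: 325 × π × (0.95 − Se)
- benign patients: 325 × (1 − π) × (0.85 − 0.65)

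| π | Se | Neoplastic | Benign | All changes (of 325) | Share neoplastic |
|---|---|---|---|---|---|
| 80% | 95% | 260 × 0.00 = 0 | 65 × 0.20 = 13 | 13 (4.0%) | 0% |
| 80% | 93% | 260 × 0.02 = 5.2 | 13 | 18.2 (5.6%) | 29% |
| 80% | 90% | 260 × 0.05 = 13 | 13 | 26 (8.0%) | 50% |
| 80% | 85% | 260 × 0.10 = 26 | 13 | 39 (12.0%) | 67% |
| 85% | 90% | 276.25 × 0.05 = 13.8 | 48.75 × 0.20 = 9.75 | 23.6 (7.25%) | 59% |
| 90% | 90% | 292.5 × 0.05 = 14.6 | 32.5 × 0.20 = 6.5 | 21.1 (6.5%) | 69% |

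At 80% neoplasia the endpoint triples, from 4.0% to 12.0%, as sensitivity falls from 95% to 85%. The number of benign patients correctly spared stays at 13 throughout.

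**Pooling with screening.** Screening prevalence is not given. Over an assumed 2% to 10%, with the same accuracy figures and Se = 90%, screening contributes 0.3 neoplastic and 63.7 benign switches (at 2%) to 1.6 and 58.5 (at 10%). The neoplastic share is then 0.5% to 2.7% in screening. Pooled with surveillance it is 13.3/90.0 = 15% to 14.6/86.1 = 17%, against 50% in surveillance alone. An unstratified result would dilute the problem.

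**Limits.** These are net patient-level counts for the biopsy decision only. Changes to or from treatment cannot be sized, because the documents give no rates for them.

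**The case against.** The strongest reply is that the plan already measures missed neoplasia. Non-inferiority in sensitivity is part of the surveillance primary analysis (G2), and endpoint 3(a) in Section D commits to sensitivity, specificity and both predictive values, per biopsy and per patient. A less sensitive HRME would count against the main result in the same patients. That stands. A reader might infer that the trial would conceal missed neoplasia; the documents do not support this.

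Two other strong readings also fail. One is that missed cancers would be scored as benefit. The plan speaks of change and potential impact, the target is neoplasia including dysplasia, and no biopsy is actually omitted. The other is that many switches must be wrong even if HRME performs as planned. At the 95% planning value the expected net number in neoplastic patients is zero; the large shares arise at or below the 90% limit.

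A reader might also take all patients negative on the combined strategy as moved to no biopsy, giving 26/(26 + 55.25) = 32% with neoplasia. That is one minus the strategy's negative predictive value. It includes Lugol's-negative patients, who have no HRME read and no plan to change.

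The other endpoints still do not repair this one. Clinical efficiency sees only benign patients. Diagnostic yield covers biopsies obtained, and F2 treats HRME-negative sites as not biopsied, so missed neoplasia leaves both numerator and denominator. G1 ties the original goals and sample size to the subjective read and powers the software read on overall accuracy, so no powered sensitivity test stands behind software-driven changes. Sensitivity and specificity also score the read, not the plan that follows, so no listed analysis sets changes to treatment against pathology.

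**Conclusion.** The concern holds as a limit on interpretation. As defined in Section D and G2, clinical impact measures how often plans change, not whether they improve, and at fixed specificity it increases as sensitivity falls: 4.0%, 8.0% and 12.0% at 95%, 90% and 85%, with none, half and two thirds of the switches in neoplastic patients. At 85% neoplasia and 90% sensitivity the share is 59%.

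These figures rest on 1:1 allocation, the G1 accuracy values, and an HRME-negative read leading to a plan of no biopsy. The true share depends on the sensitivity achieved and could be near zero. The point affects one secondary analysis. It does not touch the primary analysis or patient care, but it should be settled before the endpoint is used to support a claim about decisions.

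**What to change.** In G2, under clinical impact:

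- Cross-tabulate each change, from the Lugol's plan to the human-read plan and from the human-read plan to the software-read plan, by direction and by consensus histology (neoplastic or non-neoplastic).
- Report changes concordant and discordant with histology as separate proportions with 95% confidence intervals, by risk group and by read, beside the raw change rate.
- State the unit of analysis (site or patient) and how a patient with both kinds of change is counted.
- Do not collapse the result into an equal-weight net score. With 13 changes of each kind it would report zero, and it would treat a missed neoplasia and a spared biopsy as equal, a value judgement the plan does not argue for.
- Show changes to or from treatment by histology, without a rule for when treatment is appropriate.

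The tabulation is within the HRME group. F2 describes only one recorded plan in the Lugol's-alone group, so what counts as a change there for the between-arm test is a separate question that this fix does not settle.

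Cost: new G2 wording and a little more tabulation. No new data, patients or procedures are needed, because the plans are recorded and every Lugol's-abnormal area has histology. The headline impact figure is likely to look less favourable.
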